2.3. Study Design

This is a Phase 3, observer-blinded study to evaluate the safety, tolerability, and immunogenicity of selected when administered in combination with BNT162b2 (Omi XBB.1.5) compared to a licensed inactivated QIV administered in the deltoid opposite to that used for administration of BNT162b2 (Omi XBB.1.5) in healthy adults 18 through 64 years of age. Additionally, the study will evaluate administration of combination with BNT162b2 (Omi XBB.1.5) in comparison to standalone administration of QIV, and BNT162b2 (Omi XBB.1.5). The vaccine candidates are divided into cohorts, where approximately 8550 total participants 18 through 64 years of age will be enrolled into 1 of 3 cohorts:

Cohort 1: Approximately 450 participants randomized in a 2:1 ratio by site-based randomization to 1 of the following:

- Arm A: CCI BNT162b2 (Omi XBB.1.5) administered in the right deltoid and placebo administered in the left deltoid, concurrently.
- Arm B: 30 μg BNT162b2 (Omi XBB.1.5) administered in the right deltoid and licensed QIV (CCI administered in the left deltoid, concurrently.

Enrollment of Cohort 1 will be paused in the IRT system after the randomization of approximately 450 participants into Cohort 1. Safety data (including e-diary data, SAEs, AEs, and AESIs) of approximately 450 vaccinated participants will be evaluated by the EDMC after 60 days

Cohort 2: Approximately 4500 participants randomized in a 2:1 ratio by site-based randomization to 1 of the following:

- Arm C: CCI /BNT162b2 (Omi XBB.1.5) administered in the right deltoid and placebo administered in the left deltoid, concurrently.
- Arm D: 30 μg BNT162b2 (Omi XBB.1.5) administered in the right deltoid and licensed QIV

Cohort 3: Approximately 3600 participants 18 through 64 years of age will be enrolled and randomized in a 2:2:1:1 ratio by site-based randomization to 1 of the following:

- Arm E: CCI /BNT162b2 (Omi XBB.1.5) administered in the right deltoid.
- Arm F: 30 μg BNT162b2 (Omi XBB.1.5) administered in the right deltoid.
- Arm G: licensed QIV CCI administered in the right deltoid.
- Arm H: CCl administered in the right deltoid.

Prespecified local reaction and systemic event data will be collected in an e-diary for 7 days, or longer for ongoing symptoms, after study intervention administration (ie, from Day 1, the day of vaccination, until symptom resolution). Blood samples of approximately 20 mL will be collected for immunogenicity assessments prior to vaccination and at 4 weeks and 6 months after vaccination.

CC

Following vaccination, AEs will be collected from informed consent signing through Visit 2, and SAEs will be collected from informed consent signing through Visit 3. In addition, AEs occurring up to 48 hours after blood draws that are related to study procedures will also be collected and for collection of AESIs refer to Section 8.4.8 of the protocol.

3. ENDPOINTS AND BASELINE VARIABLES: DEFINITIONS AND CONVENTIONS

3.1. Primary Endpoint(s)

3.1.1. Safety Endpoints

In participants receiving at least 1 dose of study intervention, the safety primary endpoints are as follows:

- Local reactions (redness, swelling, and pain at the injection site) for up to 7 days following vaccination in the right deltoid only.
- Systemic events (fever, vomiting, diarrhea, headache, fatigue, chills, new or worsened muscle pain, and new or worsened joint pain) for up to 7 days following vaccination.
- AEs from vaccination through 4 weeks after vaccination.
- SAEs from vaccination through 6 months after vaccination.

3.1.1.1. Local Reactions and Systemic Events

The local reactions, including redness, swelling, and pain at the injection site, are reported in the e-diary and/or CRF from Day 1 through Day 7 after study vaccination, where Day 1 is the day of vaccination. Local reactions will be assessed at the injection site on the right deltoid only after vaccinations given at Visit 1. This section describes derivations with details for the assessment of reactogenicity data: presence of event, severity level, duration, and onset day.

Presence or Absence

For each local reaction and any local reaction on any day, Table 2 defines the algorithm to derive the presence of a reaction (yes or no) during the interval from Day 1 through Day 7, where Day 1 is the day of study vaccination.

Table 2. Derived Variables for Presence of Each and Any Local Reaction Within 7 Days for Each Dose

| Variable | Yes (1) | No (0) |
|---|--|---|
| Presence of each local reaction on any day | Participant reports the reaction as "yes" on any day (Day 1 through Day 7) | Participant reports the reaction as "no" on all 7 days (Day 1 through Day 7) or as a combination of "no" and missing on all 7 days (Day 1 through Day 7) |
| Presence of any local reaction on any day | Participant reports any local reaction as "yes" on any day (Day 1 through Day 7) | For all 3 local reactions, participant reports "no" on all 7 days (Day 1 through Day 7) or as a combination of "no" and missing on all 7 days (Day 1 through Day 7) |

Note: Completely missing reactogenicity data will not be imputed. Participants with no reactogenicity data reported will not be included in the reactogenicity summaries.

Severity and Maximum Severity

Redness and swelling will be measured and recorded in measuring device units (range: 1 to 21) and then categorized during analysis as absent, mild, moderate, or severe based on the grading scale in Table 3. Measuring device units can be converted to centimeters according to the following formula: 1 measuring device unit = 0.5 cm. Pain at the injection site will be assessed by the participant as absent, mild, moderate, or severe according to the grading scale in Table 3.

Table 3. Local Reaction Grading Scale

| | Mild (Grade 1) | Moderate (Grade 2) | Severe (Grade 3) ^a | Potentially Life-Threatening (Grade 4) ^b |
|-------------------------------|----------------------------------|--------------------------|----------------------------------|---|
| Pain at the injection site | Does not interfere with activity | Interferes with activity | activity | Emergency room visit or hospitalization for severe pain |

| | Mild (Grade 1) | Moderate (Grade 2) | Severe (Grade 3)ª | Potentially Life-Threatening (Grade 4) ^b |
|----------|--|--|---|---|
| Redness | >2.0 cm to 5.0 cm (5 to 10 measuring device units) | >5.0 cm to 10.0 cm (11 to 20 measuring device units) | >10 cm (≥21 measuring device units) | Necrosis or exfoliative dermatitis |
| Swelling | >2.0 cm to 5.0 cm (5 to 10 measuring device units) | >5.0 cm to 10.0 cm (11 to 20 measuring device units) | >10 cm (≥21 measuring device units) | Necrosis |

Table 3. Local Reaction Grading Scale

- a. If a Grade 3 local reaction is reported in the reactogenicity e-diary, a telephone contact should occur to ascertain further details and determine whether a site visit is clinically indicated.
- b. Only an investigator or medically qualified person is able to classify a participant's local reaction as Grade 4. If a participant experiences a confirmed Grade 4 local reaction, the investigator must immediately notify the sponsor. Grade 4 local reactions will be collected on the CRF.

For each local reaction or systemic event after vaccination, the maximum severity grade will be derived for the collection period (Day 1 through Day 7, where Day 1 is the day of vaccination) as follows:

maximum severity grade = highest grade (maximum severity) within 7 days after vaccination (Day 1 through Day 7) among severity grades where the answers are neither "no" nor missing for at least 1 day during the interval from Day 1 through Day 7.

Duration (First to Last Day Reported)

The duration (days) of each local reaction will be calculated as the number of days from the start of the first reported reaction to the resolution of the last reported reaction, inclusive (last day of reaction – first day of reaction + 1), after vaccination. The resolution day is defined as the last day on which the reaction or event is recorded in the e-diary or CRF. For a reaction or event collected in multiple sources, the earliest start date and the latest end date will be used in calculating duration. If there is no known resolution/end date, the duration will be reported as "unknown" and set to "missing."

Onset Day

The onset day of each local reaction will be derived. Onset day is defined as the first day of reporting a reaction of any severity after vaccination. Change in severity during the event does not impact the originally determined onset day. For example, for the onset day of each local reaction, if participants report a change in severity of the local reaction, only the first day of reporting that specific local reaction will be counted.

For a reaction collected in multiple sources, the earliest date of reporting the reaction will be used in calculating the onset day.

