#### 8.10.5. Unscheduled Visit for a Grade 3 or Suspected Grade 4 Reaction

If a Grade 3 local reaction in the right arm (Section 8.3.4.2), systemic event (Section 8.3.4.3), or fever (Section 8.3.4.4) is reported in the reactogenicity e-diary, a telephone contact should occur to ascertain further details and determine whether a site visit is clinically indicated. If a suspected Grade 4 local reaction in the right arm (Section 8.3.4.2), systemic event (Section 8.3.4.3), or fever (Section 8.3.4.4) is reported in the reactogenicity e-diary, a telephone contact or site visit should occur to confirm whether the event meets Grade 4 criteria.

A site visit must be scheduled as soon as possible to assess the participant unless any of the following is true:

- The participant is unable to attend the unscheduled visit.
- The local reaction/systemic event is no longer present at the time of the telephone contact.
- The participant recorded an incorrect value in the reactogenicity e-diary (confirmation of a reactogenicity e-diary data entry error).
- The PI or authorized designee determined it was not needed.

This telephone contact will be recorded in the participant's source documentation and the CRF.

If the participant is unable to attend the unscheduled visit, or the PI or authorized designee determined it was not needed, any ongoing local reactions/systemic events must be assessed at the next study visit.

During the unscheduled visit, the reactions should be assessed by the investigator or a medically qualified member of the study staff, such as a study physician or a study nurse, as applicable to the investigator's local practice, who will:

- Measure oral temperature (°F/°C).
- Measure minimum and maximum diameters of redness in the right arm (if present).
- Measure minimum and maximum diameters of swelling in the right arm (if present).
- Assess injection site pain in the right arm (if present) in accordance with the grades provided in Section 8.3.4.2.
- Assess systemic events (if present) in accordance with the grades provided in Section 8.3.4.3.
- Assess for other findings associated with the reaction and record these on the CRF if appropriate.

The investigator or an authorized designee will complete the unscheduled visit assessment page of the CRF.

Note: Any left arm reactogenicity event should be collected in the CRF on the AE log page.

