## 9.3.2. Primary Endpoints/Estimands Analysis

Endpoint	Statistical Analysis Methods
Safety	
 
Descriptive statistics will be provided for each reactogenicity endpoint for each vaccine group within each cohort. Local reactions and systemic events from Day 1 through Day 7 after each vaccination (where Day 1 is the day of vaccination) will be presented by severity and cumulatively across severity levels. Descriptive summary statistics will include counts and percentage of participants with the indicated endpoint and the associated 2-sided 95% CIs based on Clopper-Pearson method.
 

	
 
AEs and SAEs will be categorized according to MedDRA terms. Counts, percentage, and associated 2-sided 95% CIs based on Clopper-Pearson method of AEs from vaccination (Day 1) through 4 weeks after vaccination, and SAEs from vaccination (Day 1) through 6 months after vaccination will be provided for each vaccine group within each cohort.
 

	The safety data are summarized within each cohort but may also be summarized descriptively across cohorts as specified in the SAP.
Immunogenicity (Cohort 2)	GMR of HAI titers for each matched seasonal strain     4 weeks after study vaccination in participants who received     BNT162b2 (Omi XBB.1.5) to those who received BNT162b2     (Omi XBB.1.5) administered concomitantly with QIV.

[figure not shown]
Endpoint	Statistical Analysis Methods				
	The difference in percentages of participants with seroconversion to the seasonal strain (CCI) at 4 weeks after study vaccination between participants who received CCI BNT162b2 (Omi XBB.1.5) and those who received BNT162b2 (Omi XBB.1.5) administered concomitantly with QIV.				
	GMR of SARS-CoV-2 Omicron (XBB.1.5)—neutralizing titers at 4 weeks after study vaccination in participants who received BNT162b2 (Omi XBB.1.5) to those who received BNT162b2 (Omi XBB.1.5) administered concomitantly with QIV.				
	The difference in percentages of participants with seroresponse to SARS-CoV-2 Omicron (XBB.1.5) strain at 4 weeks after study vaccination between participants who received BNT162b2 (Omi XBB.1.5) and those who received BNT162b2 (Omi XBB.1.5) administered concomitantly with QIV.				
	
 
GMRs and the associated 2-sided 95% CIs will be calculated using the method described in Section 9.3.1.4 Unadjusted GMRs will be the primary approach. Adjusted GMRs will also be summarized as supportive.
 
				

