6.1.1.1.1. Main Analysis

- Estimand(s): Percentages of participants with local reactions and systemic events for up to 7 days after study vaccination (Section 3.1) in each vaccine group.
- Analysis set(s): Safety population (Section 4).
- Analysis time point(s): Day 1 through Day 7 after vaccination.
- Statistical method(s): Descriptive summary (Section 5.2).

- Intercurrent events and missing data: Missing data will be handled as described in Section 5.3.
- Reporting results: Descriptive summaries for each and any local reaction/systemic event
 after study vaccination will be presented, by maximum severity, for each vaccine group
 within each cohort. Descriptive summary statistics will include counts and percentages of
 participants with the indicated endpoint and the associated 2-sided Clopper-Pearson
 95% CIs.

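### Does SAP Table 2 count redness or swelling that is too small to be graded as a local reaction?

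*SAP*

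**What the plan says.** In SAP Section 3.1.1.1, Table 2 sets presence of a given local reaction to yes when "Participant reports the reaction as 'yes' on any day" from Day 1 to Day 7. It sets presence to no when the seven days hold only negative answers, or negative answers mixed with missing ones. It gives no size for redness or swelling.

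The next paragraph of that section says these two reactions are recorded in device units from 1 to 21, at 0.5 cm per unit, and are then "categorized during analysis as absent, mild, moderate, or severe based on the grading scale in Table 3". In Table 3 the mild band for both is ">2.0 cm to 5.0 cm (5 to 10 measuring device units"); nothing lies below it. Maximum severity is the "highest grade (maximum severity) within 7 days after vaccination (Day 1 through Day 7) among severity grades", taken over days answered with something other than no or missing.

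Duration runs from the first to the last reported day: "The resolution day is defined as the last day on which the reaction or event is recorded in the e-diary or CRF". Onset is the first day on which a reaction of any severity is reported.

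On outputs, Protocol Section 9.3.2 says local reactions and systemic events "will be presented by severity and cumulatively across severity levels", and SAP Section 6.1.1.1.1 says the summaries "will be presented, by maximum severity, for each vaccine group" within each cohort. SAP Section 6.1.1.1.2 adds bar charts with each bar split by severity, and summaries of duration and onset as supplementary analyses.

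**The concern.** The percentage of participants with each local reaction is a primary safety endpoint, and Table 2 is offered as the algorithm for deriving it. A participant whose largest redness is 3 units and who counts as a yes would be present under Table 2, absent under the Table 3 categories, and without a maximum severity grade. The percentage with redness or swelling could then exceed the sum of its severity rows, and two programmers could produce different tables from the same data. Fever, the other measured reactogenicity endpoint, does have an explicit threshold (38.0°C, SAP Section 3.1.1.3), which makes the omission stand out. Duration raised a related worry: a reaction graded mild on two days could be given a duration of five because smaller sizes were reported before and after.

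**Working it through.** **1. Which recorded values have no grade.** Inputs: range 1 to 21 units and 0.5 cm per unit (SAP Section 3.1.1.1); cut-offs of more than 2.0, 5.0 and 10 cm (SAP Table 3). Size in cm = 0.5 × units.

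| Units | Size (cm) | Category |
|---|---|---|
| 1–4 | 0.5–2.0 | below mild, so absent |
| 5–10 | 2.5–5.0 | mild |
| 11–20 | 5.5–10.0 | moderate |
| 21 | 10.5 | severe |

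This reproduces the unit bands printed in Table 3. Four of the 21 recordable values fall below mild. That they are absent is an inference, but absent is the only category left.

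**2. Two hypothetical diaries.** Duration = last day − first day + 1.

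| Units by day | Any recorded size counts | Only 5 units or more counts |
|---|---|---|
| 3, 4, 2, then none | present, duration 3 − 1 + 1 = 3 days | absent, no duration |
| 3, 6, 7, 4, 2, then none | present, mild, duration 5 − 1 + 1 = 5 days | present, mild, duration 3 − 2 + 1 = 2 days |

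Only the first diary makes presence and severity disagree. In the second, presence and maximum grade are the same under both readings.

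**3. Size per affected participant.** Planned arms: 4500 at 2:1 gives 3000 and 1500 (Cohort 2); 3600 at 2:2:1:1 gives 1200, 1200, 600 and 600 (Cohort 3). One participant is worth:

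- Arm C: 1/3000 = 0.033 percentage points
- Arm D: 1/1500 = 0.067
- Arms E and F: 1/1200 = 0.083
- Arms G and H: 1/600 = 0.167

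Participants with no reactogenicity data are left out of the summaries, so actual denominators may be a little smaller. These figures are only 1/N and say nothing about how many participants are affected. As an assumption, suppose 10% have a reaction of at least mild grade and a further 1%, 5% or 10% report only 1 to 4 units. The literal presence row would then read 11%, 15% or 20% against severity rows summing to 10%. None of these rates comes from the documents.

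**4. What the plan implies for the reported row.** Three statements bear on it. Measured sizes are turned into four categories during analysis, one of which is absent. Each and any reaction is tabulated by maximum severity. The total is cumulative across severity levels, so it is by construction the sum of those levels. A participant with at most 4 units contributes to no level and so not to the total. Table 2 agrees with this as soon as yes is taken to mean a measured size not categorized as absent.

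**5. Duration.** The SAP defines duration by reported days, and says so in the heading of that rule. This matches data collection: Protocol Sections 8.3.4, 8.10.2 and 8.10.3 follow ongoing symptoms to resolution and record stop dates. The documents do not say that daily sizes are recorded after Day 7, so an end day based on size might not be derivable for longer reactions.

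**The case for a change.** The best case for a change is that Table 2 should be complete on its own terms. It is presented as the derivation rule for a primary endpoint, it omits the one step that matters for a measured reaction, and neither document supplies that step elsewhere; Protocol Section 8.3.4.2 repeats the range and the scale without it. If a threshold of 5 units is intended, writing it down would cost almost nothing.

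The factual part stands: yes is not defined for redness and swelling, and the arithmetic is right. What does not stand is that the omission leaves the result open. The discrepancy needs Table 2 to be read apart from the paragraph after it and from the reporting rules in both documents. It also needs a yes recorded for sizes of 1 to 4 units, and the documents do not show whether the participant answers such a question or whether yes is derived from the size. If the literal reading were programmed, the total would differ from the sum of its severity rows, or the bar from its segments, which an ordinary table check would expose.

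The duration argument is weaker. A mild reaction reported for five days contradicts nothing in the severity rows; the two variables measure different things. A grade-based rule would also need choices the plan does not now require. At an unscheduled visit, for example, staff "Measure minimum and maximum diameters of redness in the right arm", and such a rule would have to say which diameter counts.

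**Conclusion.** This is a missing definition that analysts following the plan would fill correctly, and no change is needed. The graded outputs in Protocol Section 9.3.2 and SAP Sections 6.1.1.1.1 and 6.1.1.1.2, with absent as an analysis category in SAP Section 3.1.1.1, lead to counting redness and swelling from 5 units upward.

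This assumes that the diary or derivation specification, which the documents do not show, treats sizes below mild as absent. If it does, the effect is zero. If it does not, the effect is 0.033 to 0.167 percentage points per affected participant across Cohorts 2 and 3, with an unknown number affected. It would be confined to the redness and swelling rows, plus the any-local-reaction row for participants with no pain and no graded reaction. Pain is graded directly by the participant and is not affected. The endpoint is descriptive, so no hypothesis, margin, alpha or sample size depends on it. Keeping duration on reported days is a reasonable choice that fits how the data are collected.

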3.1.1.2. Systemic Events

The systemic events, including vomiting, diarrhea, headache, fatigue, chills, new or worsened muscle pain, and new or worsened joint pain, are assessed and recorded in the e-diary and/or CRF from Day 1 through Day 7, where Day 1 is the day of vaccination. The derivations for systemic events will be handled in a way similar to the handling of local reactions with respect to presence of event, severity level, duration, and onset day (see Section 3.1.1.1).

The systemic events will be assessed as mild, moderate, or severe according to the grading scale in Table 4.

Table 4. Systemic Event Grading Scale

| | Mild (Grade 1) | Moderate (Grade 2) | Severe (Grade 3)ª | Potentially Life-Threatening (Grade 4) ^b |
|--------------------------------|------------------------------------|------------------------------------|---------------------------------------|---|
| Vomiting | 1-2 times in 24 hours | >2 times in 24 hours | Requires IV hydration | Emergency room visit or hospitalization for hypotensive shock |
| Diarrhea | 2 to 3 loose stools in 24 hours | 4 to 5 loose stools in 24 hours | 6 or more loose stools in 24 hours | Emergency room visit or hospitalization for severe diarrhea |
| Headache | Does not interfere with activity | Some interference with activity | Prevents daily routine activity | Emergency room visit or hospitalization for severe headache |
| Fatigue/tiredness | Does not interfere with activity | Some interference with activity | Prevents daily routine activity | Emergency room visit or hospitalization for severe fatigue |
| Chills | Does not interfere with activity | Some interference with activity | Prevents daily routine activity | Emergency room visit or hospitalization for severe chills |
| New or worsened muscle pain | Does not interfere with activity | Some interference with activity | Prevents daily routine activity | Emergency room visit or hospitalization for severe new or worsened muscle pain |
| New or worsened joint pain | Does not interfere with activity | Some interference with activity | Prevents daily routine activity | Emergency room visit or hospitalization for severe new or worsened joint pain |

a. If a Grade 3 systemic event is reported in the reactogenicity e-diary, a telephone contact should occur to ascertain further details and determine whether a site visit is clinically indicated.

b. Only an investigator or medically qualified person is able to classify a participant's systemic event as Grade 4. If a participant experiences a confirmed Grade 4 systemic event, the investigator must immediately notify the sponsor. Grade 4 systemic events will be collected on the CRF.

